#### 4. STUDY DESIGN

**Aim 1:** We will conduct a mixed-methods study (quantitative and qualitative). Eight AYA with SCD ages 13-21 will participate in the *SCThrive* six-week, mixed format (in-person and online) intervention. Participants will complete measures at baseline and post-intervention to assess feasibility and acceptability of data collection and management procedures. We will also obtain qualitative feedback (via focus groups) from participants about *SCThrive* content, format, feasibility and acceptability. Data will be used to refine and finalize the intervention protocol.

**Aim 2:** We will conduct a pilot 2-arm randomized controlled trial to test the initial efficacy of *SCThrive* in improving BA relative to an Attention Control in AYAS with SCD ages 13-21. AYA with SCD will first be dichotomized by age (13-17 and 18-21) and disease severity (severe/non-severe). Participants will be categorized as severe if they have a history of acute chest syndrome, prior stroke or more than three hospitalizations for vaso-occlusive crises in the prior 3 years. Participants will be categorized as not severe if these complications are not present. Participants within each of the 2 (age; 13-17 years or 18-21 years) by 2 (disease severity; severe or not severe) cells will be randomized into the *SCThrive* intervention arm or an attention control arm (e.g., stratifying participants based on age and disease severity prior to random assignment).

Study participation includes a baseline assessment, after which participants will be randomized to the *SCThrive* intervention arm or attention control arm. This is followed by 6 weeks of intervention (*SCThrive*) and post-treatment assessment. Given the grant timeline, only a subset of participants will be followed in the post-treatment period. Fourteen *SCThrive* intervention arm participants will complete an online/in-person booster session at 6 weeks post-treatment and 14 attention control participants (N=14) will receive a follow-up phone call at 6 weeks post-treatment. These participants will also complete a follow-up assessment 6 weeks after treatment ends.

Our **primary outcome** will be for participants in the *SCThrive* group to demonstrate greater BA at post-treatment than the attention control group. Our **secondary outcome and exploratory aim** will be greater improvements in self-management behaviors and quality of life at the six-week follow-up.

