**Table 3. Assessment Strategy**

Construct	Measure	Brief Description/Score Used/ Psychometrics
Primary Outcome Measure		
Behavioral Activation (BA) (AYA report)	PAM-13 	Measures skills, knowledge, confidence and readiness for self-management; Total Score; used in many studies of BA and self-management  ; $\alpha = .87$
Secondary and Exploratory Outcome Measures		
Self-management behaviors (AYA report)	TRAQ-5  ; Youth Risk Behavior Survey items 	Measures managing medications and appointments, tracking symptoms, provider communication, daily interference and physical activity, eating, sleeping and fluid intake; TRAQ Total Score ( $\alpha = .82-.92$ ) and Youth Risk Behavior Survey item mean scores; N/A
Self-management behaviors (clinician rating)	TRxANSIT Scale V4 	Semi-structured interview that assesses knowledge of chronic health condition, medications, adherence, nutrition, self-management skills, insurance, and finding a new health care provider); Knowledge of Chronic Health Condition, Medications, Adherence, Self-Management Skills Subscales; $r = .71$
Medication Adherence (clinician rating)	Medical Adherence Measure (MAM) 	Semi-structured interview with four general modules to assess adherence with medication, diet, exercise, and clinic attendance; Medication Domain; $r = -.40$ ; $r = .89$
SCD-specific quality of life (Caregiver & AYA report)	Peds-QL SCD Module 	Measures several domains of health-related quality of life including pain impact, fatigue, pain management, emotions, communication and treatment adherence; Total Score; $\alpha = .95$
SCD Knowledge (AYA report)	SCD Knowledge Questionnaire 	Measures SCD knowledge including pathophysiology, treatments and self-management; Total Score; $\alpha = .79$
SCD Self-Efficacy (AYA report)	Sickle Cell Self-Efficacy Scale 	SCD self-efficacy scale validated in adolescents with SCD; Total Score; $\alpha = .87$
Self-Regulation (AYA Report)	Treatment Self-Regulation Questionnaire (TSRQ)	Measures the degree of motivation an individual has towards changing/maintaining health behaviors; Total Score; $\alpha > .73$ .
SCD Transition Readiness	Transition Intervention Program Readiness for Transition (TIP-RFT)	Measures healthcare knowledge and skills, education and vocation planning, social support skill set, and independent living skills.

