## 9. DATA ANALYSIS/METHODS

**Analytic Plan.** We will use Mplus (Version 7.20) to conduct our analyses. Descriptive statistics (e.g. proportions for dichotomous variables, means, and standard deviations) will be calculated for all measures of interest. Outliers will be examined and kept in final analyses, unless substantial evidence is available for their deletion (e.g., data errors). When testing statistical hypotheses, statistical model assumptions will be examined.

**Aim 1: Determine the feasibility and acceptability of the SCThrive intervention for adolescents and young adults with SCD.** **Feasibility** of SCThrive will be assessed by the proportion of eligible patients approached for the study who consent to participate and attend at least 4/6 sessions. **Acceptability** will be assessed by qualitative analysis of focus groups at the end of treatment. The focus groups will elicit the AYAs overall impression of the program, the mixed format, how well they perform skills, and the progression of activities, as well as content- and format-specific feedback on the integration of iManage and SCD content, interest level, and length of sessions.

**Aim 2: Conduct a pilot randomized trial (final N=54 assuming 15% attrition) to determine whether the refined SCThrive intervention is superior to attention control in improving BA in AYAs with SCD ages 13-21.** A 2 (group; treatment vs. control) by 2 (time; Pre-/Post-test) mixed ANCOVA analysis will be used, with BA (PAM-13) as our primary outcome, time and group as main effects, and a time\*group interaction effect, to determine the needed effect size estimates. The statistical test of the interaction will be the primary tests of the efficacy of the SCThrive intervention. If statistically significant, the group\*time interaction would indicate BA changed differently across time between the two groups and effect sizes (d) will be calculated

for all significant simple main effects and simple comparison effect size calculations described above.

**Exploratory Aim:** A MANOVA will be used to test for significant group (*SCThrive* vs. attention control) differences on improvements in self-management behaviors and quality of life scores at three months. A significant omnibus test will be followed with simple comparisons and computation of effect size estimates (d).

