### **15. PRIVACY & CONFIDENTIALITY**

The informed consent process will address various aspects of participant privacy including the level of control over the circumstances and extent of sharing one's personal information. As stated above, participants will only be approached by study personnel after initial interest is obtained through their provider. The nature of the intervention (e.g. group self-management sessions) leads to a loss of privacy as participants will be able to identify each other. They may also be identified by others if a participant logs onto the group video chat in a public location. This will be explained to participants as a compromise of the security of the data and part of the consent form. If a participant logs on from a public place, the clinical research coordinator will end the call with the participant and call them individually to problem solve an alternate location. If a suitable private location cannot be found, the participant will be asked to turn off their webcam and participate by phone or set an appointment to review the recorded session at a later date. During the informed consent process, the study personnel will explain these risks and the nature of the interaction with other participants. At that time, the potential participant may 1) decline to participate or 2) agree to participate with the understanding that they may withdraw at any time. This will give the participant control over the circumstances of sharing their personal information. To minimize privacy risks, all participants will also be required to sign an agreement that the AYA will log on to sessions from a private location. Study personnel will screen all questionnaires for completeness; participants are allowed to skip any survey questions they do not wish to answer, thereby providing additional control over the extent of sharing personal information.

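### The exploratory aim plans arm comparisons and effect sizes only after a significant omnibus MANOVA, in at most 28 people, so the estimates a pilot needs may never be produced

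*Combined protocol and SAP*

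**What the plan says.** Section 9, Exploratory Aim: "A MANOVA will be used to test for significant group" (the two arms) "differences on improvements in self-management behaviors and quality of life scores at three months". The next step is conditional: "A significant omnibus test will be followed with simple comparisons and computation of effect size estimates". No alpha, power figure, list of dependent variables or missing-data rule is given for this analysis.

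Section 4 restricts who reaches this assessment: "only a subset of participants will be followed in the post-treatment period". Fourteen SCThrive participants have the booster and the follow-up assessment, and in the other arm "14 attention control participants (N=14) will receive a follow-up phone call at 6 weeks post-treatment", also with that assessment. Section 17.3 repeats the figure of 14 for the SCThrive arm.

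Table 3 gives the self-management measures as the TRAQ total, Youth Risk Behavior Survey item mean scores and, from the clinician-rated TRxANSIT interview, the "Knowledge of Chronic Health Condition, Medications, Adherence, Self-Management Skills Subscales". Quality of life is the PedsQL SCD total. Section 8 schedules the caregiver version only at baseline and post-treatment, so the AYA version alone is available at follow-up.

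Section 9 also promises means and standard deviations for all measures, without any condition.

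**The concern.** Section 2 asks whether SCThrive is associated with greater improvements than control, and section 1 presents the study as groundwork for a larger trial. Both call for an estimated difference between arms on each score, with its uncertainty, whatever the p-value. The plan makes the comparisons and d depend on a single multivariate test in at most 28 people.

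Three things are at stake. The gate may well close even if the intervention helps. The omnibus test responds to any departure from equal mean vectors, so a mixed pattern can open the gate more readily than consistent benefit. And effect sizes reported only after a significant result tend to be too large, which is unhelpful when they feed the design of the next trial.

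**Working it through.** **The plan's own figure.** The only stated power is for the primary PAM-13 comparison (section 9, Power Analysis): above 0.80 with 27 per arm, d = 0.60 and R² = 0.40. The residual SD is √0.60 = 0.775, so the standardised effect is 0.60/0.775 = 0.775. Then 0.775 × √(27/2) = 2.846, and Φ(2.846 − 1.96) = 0.81. This reproduces. There is no corresponding figure for the MANOVA.

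**Inputs for the exploratory aim.**
- n = 14 per arm, N = 28 (sections 4 and 17.3).
- Number of scores p, from Table 3: TRAQ 1 + Youth Risk Behavior at least 1 + TRxANSIT 4 + AYA PedsQL 1 = 7. Adding the Medical Adherence Measure makes 8; entering several Youth Risk Behavior items makes about 10. A narrow reading (TRAQ total and PedsQL total) gives p = 2.
- Assumed, because the documents do not give them: alpha 0.05; d = 0.60 on every score (the primary outcome's increment); a common correlation ρ between scores, varied from 0 to 0.5.

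**Formula.** With two arms, MANOVA is Hotelling's T². Power comes from the noncentral F with p and N − p − 1 degrees of freedom and noncentrality (n/2) × D². For a uniform shift, D² = p·d² / (1 + (p − 1)ρ).

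Example, p = 7, ρ = 0.3: D² = 7 × 0.36 / 2.8 = 0.90; noncentrality 7 × 0.90 = 6.3; F(7, 20); power 0.29.

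Example, p = 10, ρ = 0.5: D² = 3.6 / 5.5 = 0.655; noncentrality 4.58; F(10, 17); power 0.16.

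| ρ | p = 2 | p = 7 | p = 8 | p = 10 |
|---|---|---|---|---|
| 0 | 0.46 | 0.74 | 0.76 | 0.78 |
| 0.1 | 0.42 | 0.50 | 0.49 | 0.46 |
| 0.2 | 0.39 | 0.37 | 0.35 | 0.31 |
| 0.3 | 0.36 | 0.29 | 0.27 | 0.23 |
| 0.5 | 0.32 | 0.21 | 0.19 | 0.16 |

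A simulation of 60,000 datasets at p = 8, ρ = 0.5 gave 0.189 against 0.190 from the formula.

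**Comparator.** A two-sided t test of one score with 14 per arm and d = 0.60 has power 0.33. The MANOVA falls below this once ρ exceeds 0.24 (p = 7), 0.21 (p = 8) or 0.18 (p = 10).

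**Sensitivity.**
- Loss to follow-up: with the plan's 15% attrition, 14 × 0.85 ≈ 12 per arm. Power for 7 to 10 scores is then 0.23 to 0.18 at ρ = 0.3 and 0.17 to 0.13 at ρ = 0.5; a single score has 0.29.
- Smaller effect, d = 0.40: 7 to 10 scores give 0.23 to 0.20 at ρ = 0.1 and 0.11 to 0.09 at ρ = 0.5.
- Larger effect, d = 0.90: 0.45 to 0.35 at ρ = 0.5, against 0.63 for a single score; the break-even ρ is 0.30 to 0.23.

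**Direction.** Take p = 8 with all scores oriented so that higher is better. If four scores are better and four worse by 0.60, D² = 8 × 0.36 / (1 − ρ). At ρ = 0.3 this is 4.11 (noncentrality 28.8, power 0.91); at ρ = 0.5 it is 5.76 (noncentrality 40.3, power 0.98). Uniform benefit of 0.60 gives 0.27 and 0.19 at the same correlations.

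**Precision without the gate.** The unadjusted 95% CI half-width is 2.056 × √(2/14) = 0.78 SD.

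**The case against.** This is a labelled exploratory aim in a pilot, and section 9 itself says that measures other than the PAM-13 may need longer to respond. Low power is expected, and is not in itself a fault. That stands, but it is a reason to estimate freely, not to make estimation depend on a test.

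Four stronger readings are tempting, and the documents do not support them.

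- A reader might infer that MANOVA is always weaker than a single-score test. That depends on correlations which the documents do not give. With uncorrelated scores all moving by 0.60, seven scores give 0.74 against 0.33. Correlations above 0.2 are plausible, since four scores are subscales of one interview and the scales overlap in content, but this is a judgement.
- A reader might infer that anyone with one missing score is dropped. Section 15 does say that "participants are allowed to skip any survey questions they do not wish to answer", but the same sentence has staff screen questionnaires for completeness. The plan states no deletion rule, and it names Mplus, which can fit incomplete data by maximum likelihood. What can be said is that the missing-data rule is absent.
- A reader might infer that the analysis cannot show direction. The omnibus test cannot, but the simple comparisons and d planned after a significant result would.
- A reader might infer that nothing is seen if the gate closes. Means and standard deviations are promised regardless; what is lacking is a planned difference, interval or d.

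The score count is also inferred, and a two-score reading is possible. Power is then 0.46 to 0.32, close to or above that of a single test, yet still below one half.

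Finally, Holm adjustment is no route to high power either. At its first step (0.05/7 or 0.05/10) an unadjusted test of a given score has power of about 0.11 or 0.09. The case for the change rests on estimation, not on easier significance.

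**Conclusion.** The concern holds in a limited form. The gate is explicit in section 9, and 28 is the most that can be analysed. If d = 0.60 on every score and alpha is 0.05, the gate fails more often than not for 7 to 10 scores at correlations of 0.2 or more (power 0.37 to 0.16), is about even at 0.1 (0.50 to 0.46), and usually opens if the scores are uncorrelated. On the two-score reading it fails more often than not at every correlation from 0 to 0.5. When it fails, no between-arm estimate is planned for a pilot whose purpose is to inform a larger trial. The test is also poorly matched to a directional aim: with 8 scores and correlations of 0.3 to 0.5, it detects a half-better, half-worse pattern 91 to 98% of the time and uniform benefit 27 to 19% of the time. Alpha, effect size, correlations and the number of scores are assumptions or inferences. The finding does not depend on any claim about deletion of incomplete cases.

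**What to change.** Remove the omnibus gate. List in the SAP each Table 3 self-management score and the AYA PedsQL total that belong to this aim. For each, fit a separate linear model of the follow-up score on arm, that score's baseline and the randomisation strata (age group and disease severity), using everyone who has that score, and state how missing values are handled. Report every arm difference and d with a 95% CI, labelled exploratory, whatever the p-value. Apply Holm across the listed scores only if a p-value is to be claimed as significant.

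The data are already planned, so the cost is SAP wording. The single global p-value is lost, and the report must carry several imprecise estimates, which the intervals will show plainly.

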## 11. POTENTIAL BENEFITS

Based on our prior work with group self-management interventions, we expect that *SCThrive* participants will most likely experience direct benefits including improved behavioral activation, self-management, better ability to cope and improved mood and functioning. In addition, all participants may receive some benefit from completing disease self-management measures. If successful, this line of research has the potential to significantly impact clinical care for all AYAs suffering from SCD and improve their psychological and physical health outcomes.

## 12. POTENTIAL RISKS, DISCOMFORTS, INCONVENIENCES, AND PRECAUTIONS

Overall, this study presents minimal risk to participants. To further minimize risks and protect participants' confidentiality, all members of the study team will have completed mandated training procedures and certifications. Specific risks are noted below.

1. **Emotional/clinical distress.** Asking AYA with SCD to complete self-report measures about their symptoms, physical and psychological functioning typically does not result in distress. However, some AYA may report depressive affect or suicidal thoughts or become emotionally distressed when discussing their disease self-management.
2. **Hassles/frustrations.** It is possible that teens may not like the *iManage* app or receiving messages (electronic reminders) from other group members or the individual they designate for their secondary reminder.
3. **Confidentiality & Privacy.** The primary risk of this study is the loss of confidentiality in three main ways: 1) considering focus groups and the group-based intervention involve collaboration and support among the participants, there is an inherent loss in privacy between group members; 2) loss of confidentiality or privacy that may occur if participants log onto to the group video chat from a public or semi-public location; 3) inadvertent and unauthorized release of PHI to individuals outside the study or research team.

### ***Protections Against Risk***

1. **Emotional Distress.** In the event that a participant becomes emotionally distressed during their study participation or a participant reveals severe depressive symptoms or suicidal ideation (e.g. on the Beck Depression Inventory-II), the PI ([name], a licensed psychologist) will be immediately notified. A risk assessment, including detailed information about suicidal ideation, intent and/or plans, access to means to hurt themselves, major stresses, availability of social supports, access to treatment, and plans for safety will be discussed in detail with the subject. The assessment will be conducted by either the PI or [name], also a licensed clinical psychologist, with extensive experience in the treatment of SCD patients. A referral to the Emergency Room (if necessary), and/or a referral to the Psychiatry Division or our outpatient Psychology clinic, as appropriate, will be made. All actions taken will be documented in the participant's confidential folder. The *SCThrive* intervention will be delivered by a highly trained psychologist ([name]) and an experienced clinical psychology graduate student ([name]) supervised by the PI ([name]) who is an expert in cognitive behavioral and self-management interventions.
2. **Hassles/Frustrations.** During the consent process, participants are told of the possible hassle/frustration caused by the receipt of reminders to complete self-management goals and action plans. Study personnel will be trained to give participants the proper instructions to change the frequency, alter the sound (new ringtone, vibrate), or delete the reminders at any time. Additionally, the participant is given the contact information of a research coordinator who is able to assist them in making necessary changes to reminders.
3. **Confidentiality & Privacy.** All personnel will participate in training on protecting the rights and welfare of human participants in research. Personnel will all complete an online tutorial and satisfactorily complete an electronically-administered examination testing knowledge and application of the ethical principles and Federal regulations protecting human participants in research as described in the Belmont Report and Title 45 Code of Federal Regulations Part 46.

Adverse events will be reported to the IRB during continuing review, while serious adverse events will be reported to the IRB within 24 hours.

### **13. RISK/BENEFIT ANALYSIS**

Based on a risk/benefit judgement and our knowledge of the study procedures, the risk of adverse effects is minimal. The potential benefits to participants such as improved ability to self-manage, which lead to overall improved quality of life may outweigh any minimal risks participants may experience. The potential benefits of this study including improvement of knowledge of SCD, self-management, and quality of life in adolescents with SCD serve as justification for the minimal risks associated with this study.

### **14. DATA SAFETY & MONITORING**

This project includes a small scale clinical trial in Phase 2 and we recognize the need to provide a plan to ensure scientific integrity and safeguard the well-being of study participants. As such, the PI and research team will plan regular monthly meetings to monitor the progress of the study, the integrity of the treatment and safety monitoring, including a review of any adverse events. If participants experience any adverse events, investigators will follow up participants and provide treatment until the event has subsided. Investigators will be available 24 hours via pager. The PI will report any significant study-related or unanticipated adverse events to the Institutional Review Board and to the study sponsor based upon institutional and sponsor guidelines. Given that this study is an initial exploratory study with a single treatment arm, it is felt that monitoring at the level of the PI and research team, with oversight from the IRB and study sponsor, is sufficient.

